**National coordinator [name]**

### **Rationale**

Chronic venous disease (CVD) is widespread, underdiagnosed, and can progress to chronic venous insufficiency and venous ulcers, which can require extensive treatment and hospitalization. The global burden of CVD and its treatment are already enormous, consuming approximately 2% of national healthcare budgets.[1]

Clinical signs of CVD of lower limbs may include superficial femoral vein dilation or varicose veins, leg weakness, feeling of heaviness and/ or tenderness, edema, skin changes, venous ulcers. In addition, CVD can involve the superficial veins, traffic veins, and deep veins or even the entire lower limb venous system. This disease can be caused by primary or secondary factors, and venous reflux or proximal obstruction are the main hemodynamic changes. Due to the diversity of clinical manifestations and the complexity of pathophysiological changes, correct and timely diagnosis is the foundation to provide accurate treatment as earlier as it could be initiated. [2]

On the other hand, many patients, specifically at earlier stages of the disease, often postpone visit to a doctor. As a result, it leads to uncontrolled disease progression and further disabilities. It also can lead to trophic ulcers and other potentially dangerous complications including bleeding from varicose nodes or thromboembolic events.

Artificial Intelligence based (AI) or Neural Networks (NN) technologies have become one of the exiting areas of the scientific research and most studies in this field have been aimed at using these technologies to analyse a big massive of data to diagnose and differentiate between a large scope of conditions.[3] In diagnosis, it was shown in several studies that AI based/ NN tools demonstrated comparable with conventional methods accuracy in analysing/ diagnosing medical images, including those in the fields of dermatology and ophthalmology.[4]

Despite vast majority of studies in the mentioned field, currently there are few data available in which AI&NNs were used to segment CVD images, test them on large datasets and suggest the presence of CVD. The AIVARIX application is an AI based tool that uses machine learning in teaching the app accurately detect signs of early stages of CVD of lower limbs by photos. It has been recently published that the app is characterized by a very good interobserver agreement with conclusions (concordance score) made by experts – phlebologists in detection of C0s -C2 classes in patients with CVD. [5] However, to our knowledge no validating clinical studies have yet been done to accurately describe Sensitivity (Sn) and Specificity (Sp) of the app in outpatients so we decided to explore the accuracy (Sn and Sp) of this application in detection of early stages of CVD (C1 and C2) by CEAP in patients seeking consultancy of phlebologists for signs and symptoms indicative to mentioned conditions.

## Design

This study is a multicenter observational study, which is carried out in frame of routine clinical practice in Russia. The program will include patients suggestive to chronic venous diseases (CVDs) including but not limited to those with C1 and C2 classes by CEAP classification, who will be seeking professional phlebologists' consultation. Study conduction is scheduled in Russia in 2022-2023. The planned number of patients is 414.

Program milestones:

First Patient First Visit	Q4\2022
Last Patient Last Visit	Q3\2023
Completion of statistical analysis	Q4\2023
Clinical study report	Q4\2023

## Aim of the program

The main goal of this study is to describe the AIVARIX app accuracy in detecting C1 and C2 classes by CEAP classification of chronic venous disease (CVD) in patients who are consulted by phlebologists on symptoms and signs suggestive to CVD.

Primary goal(s):

The primary goal of the study is to estimate Sensitivity (Sn) and Specificity (Sp) of the AI-based AIVARIX app in detecting C1 and C2 classes of CVD in patients who are seeking for professional advice from a phlebologist regarding symptoms and signs suggestive to CVD.

- Sensitivity is defined as the ratio of the number of positive cases of detection of signs of C1 or C2 CVD, identified using the AIVARIX tool, to the total number of truly positive cases of C1 or C2 CVD in the study population, confirmed by phlebologists using objective / instrumental examinations.
- Specificity is defined as a proportion of the number of negative cases of signs C1 or C2 classes of CVD identified by the AIVARIX tool divided to overall truly negative cases of C1 or C2 in the study population confirmed by phlebologists by means of objective/ instrumental examination.

Once Sn and Sp of the application is estimated, positive and negative likelihood ratios (LR) will be calculated.

Secondary goal(s):

Secondary objectives are to calculate the positive and negative predictive values (PPV and NPV, respectively) of AIVARIX in detecting signs of C1 and C2 classes of chronic venous disease.

PPV is defined as the proportion of true positive cases of class C1 or C2 CVD detected using AIVARIX as a proportion of the number of true positive and false positive cases of class C 1 or C 2 identified using the AIVARIX application and confirmed by phlebologists.

The NPV is defined as the ratio of the number of true negative cases of C 1 or C 2 CVD detected using AIVARIX to the true negative and false negative cases of C 1 or C 2 CVD detected using AIVARIX and confirmed by phlebologists.

Primary Variables:

- Sensitivity and specificity of the AIVARIX app in detecting C 1 class of CVD.
- Sensitivity and specificity of the AIVARIX app in detecting C 2 class of CVD.

Secondary Variables

- PPV, NPV, LR+ and LR- of the AIVARIX app in detecting C 1 class of CVD
- PPV, NPV, LR+ and LR- of the AIVARIX app in detecting C 2 class of CVD

## Methodology

This is a cross sectional multicenter prospective observational study. It will include patients seeking phlebologist's consultation with any signs and symptoms suggestive to CVD including but not limited to C1 and C2 classes as well as patients without CVD who have other skin pathologic conditions of lower extremities that require differential diagnosis with CVD. Twenty-one phlebologists consulting in outpatient clinics across the country will be participating in the study.

The total number of patients as well as the number of patients with CVD C1 and C2 classes, the number of patients with other classes of CVD and the number of patients with other skin pathologic conditions of lower extremities are estimated given data on prevalence of CVD classes in general population available for Russia and other countries. This estimation is described in the "Sample size calculation and justification" paragraph. According to the mentioned estimation a distribution of patients to be enrolled in the study by each participating phlebologist should be as following:

- 20 subjects overall of whom:
  - 6 patients with CVD C1 class
  - 4 patients with CVD C2 class;
  - 2 patients with CVD with classes other than C1-C2 (C4-C6);
  - 8 patients with either C0s CVD or with skin pathologic conditions of lower extremities other than CVD;

Patients will be screened by a phlebologist and if meet inclusion/ non-inclusion criteria and provide written consent to participate in the study will be included in the study. Phlebologist will evaluate patients' status locales in accordance to routine clinical practice to objectively confirm or exclude presence of CVD and to define a class of the disease if present. Presence of CVD and associated class by C will be confirmed based on results of diagnostic methods used in routine clinical practice (presumably with use of objective examination, anamnesis morbi and ultrasonography of veins of lower extremities and/ or by venography of lower extremities, if necessary).

Once the clinical evaluation is made, investigating physician will take one photo of the locus with spider veins in patients present with C1 class, or with varicose veins for patients present with C2, or locus with either no signs of pathology or with pathologic condition of the skin of lower extremities other than CVD in accordance to the distribution split described herein above, and then will upload the picture to the cloud storage. Phlebologists participating in the study will also record results of the clinical evaluation for each enrolled patient in the eCRF with imputing the information on presence or absence of CVD with obligatory indication of class by C as well as presence or absence of other skin pathologic condition(s) of lower limbs that required consultation and differentiation by phlebologist. If a patient has CVD simultaneously present with signs of C1 and C2 as well as with other classes of CVD a phlebologist will have to decide which locus of pathology to picture in accordance to the given distribution of patients to be enrolled. In case a patient has no CVD but any other skin pathologic condition of lower extremities of different nature a phlebologist will take one photo of the locus with a corresponding pathologic sign(s) and then upload it to the cloud. In any cases investigating phlebologist will record information on presence or absence of CVD indicating its class or other pathologic condition in the eCRF.

Each uploaded photo must be deindividualized and should have a unique ID code assigned to each patient.

In order to fulfill minimum requirements for technical characteristics of smartphones/ pictures to be taken, following criteria are to be satisfied:

- Smartphone is to be manufactured in 2015 or later but not earlier.
- Area of the interest is to occupy not less than 30% of the picture. To fulfill this requirement a smartphone has to be positioned so that the distance from the skin area of interest to smartphone's camera is in range of 30-50 cm.
- Plain background (a picture is to be taken at the background of plain/ monochromic wall/ surface without any additional subjects in focus including additional parts of the body, furniture or people, etc.).
- Smartphone is to be positioned in parallel to the skin area of interest.

Once required number of patients is achieved and all images uploaded to the cloud storage they will be downloaded and analyzed by the AIVARIX application. For each photo the app will make a conclusion regarding possible presence or absence of CVD C1 or C2 that will be then compared with the conclusion made by an investigating physician. Eventually, based on obtained results, the Sensitivity and Specificity of the app will be established.

Additionally, to validate the tool with established Sensitivity and Specificity, a concordance between the confirmed diagnosis and signs of the app will be assessed. The Cohen's Kappa and Percentage agreement will be calculated for this purpose.

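### Class quotas without consecutive enrolment, plus a quota-guided choice of photographed site, can bias the accuracy estimates, probably upwards for sensitivity

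*Combined protocol and SAP*

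**What the plan says.** Methodology states that "Twenty-one phlebologists consulting in outpatient clinics across the country will be participating in the study" and that "a distribution of patients to be enrolled in the study by each participating phlebologist should be as following": 20 subjects each, of whom 6 are C1, 4 are C2, 2 are C4-C6, and 8 have C0s or a non-CVD skin condition of the leg. Selection is described only as "Patients will be screened by a phlebologist and if meet inclusion/ non-inclusion criteria and provide written consent", after which the patient is included. No section asks for consecutive or random enrolment or a screening log, or says what happens to eligible patients once a cell is full.

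On the photo, Methodology says: "Once the clinical evaluation is made, investigating physician will take one photo of the locus with spider veins in patients present with C1 class". It likewise names varicose veins for C2, and unaffected skin or another skin condition for the remaining patients. It sets conditions on distance, framing, background and camera angle. Where several classes coexist, "a phlebologist will have to decide which locus of pathology to picture in accordance to the given distribution of patients to be enrolled".

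Aim of the program names the target population as patients who consult a phlebologist about symptoms and signs suggestive of CVD. Section 1.12 declares bias management not applicable at the analysis stage and keeps only a review of deviations.

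**The concern.** Sensitivity and specificity depend on the spectrum of cases. Here the physician who sets the reference diagnosis also supplies the app's input, knowing the intended label and working to a quota. In a mixed-class patient the open cell, not the presenting problem, decides which lesion the app sees. In a patient with several lesions of one type, nothing says which to picture. An obvious, photogenic lesion is the natural choice.

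None of this would be a protocol deviation, so the review in section 1.12 would not detect it. The confidence intervals would not show it either, and more patients would not reduce it. Without a record of eligible patients not enrolled, it could be neither measured nor corrected afterwards. The reported accuracy might then describe selected photos rather than the consulting population named in the aim.

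**Working it through.** **1. The plan's own numbers (section 1.11).** For specificity 70% against 60%, two-sided 5%, 80% power, the Agresti-Coull approach gives 186 per half (power 0.820 on recalculation). Then 186 / 0.50 = 372, and 372 / 0.90 = 413.3, rounded up to 414. Half is 207, split 3/5 and 2/5 into 124 C1 and 83 C2. The quotas agree closely: 21 × (6, 4, 2, 8) = 126, 84, 42, 168, total 420, against 124, 83, 41, 166, total 414.

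**2. Precision of sensitivity by class.** The primary variables are class-specific. If the planned 10% loss falls evenly, 124 × 0.90 = 111.6, about 112 C1, and 83 × 0.90 = 74.7, about 75 C2. Exact (Clopper-Pearson) 95% intervals near the 80% target are:

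- C1, 90/112: 71.8% to 87.3%, half-width about 7.7 points
- C2, 60/75: 69.2% to 88.4%, half-width about 9.6 points

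**3. Size of a selection effect (assumed inputs).** The documents give no lesion-spectrum data. Suppose the app detects 90% of typical and 65% of subtle lesions, and 60% of presenting lesions are typical. With a share t of typical lesions pictured, sensitivity = 0.90t + 0.65(1 − t).

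| t | Sensitivity | Bias (points) |
|---|---|---|
| 0.60 (truth) | 80.0% | 0 |
| 0.70 | 82.5% | 2.5 |
| 0.80 | 85.0% | 5.0 |
| 0.90 | 87.5% | 7.5 |

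The bias equals the shift in t times the gap in detection: 0.10 × 25 = 2.5 points, up to 0.30 × 25 = 7.5 points. Other assumed pairs show how far this depends on the gap. As the share of borderline lesions goes from 40% to none, accuracy moves from 74% to 90% (clear 90%, borderline 50%), from 75% to 85% (85%, 60%), or from 73% to 95% (95%, 40%).

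**4. Effect on the 60% benchmark.** Section 1.11 calls 60% not acceptable. Suppose true sensitivity is 60% and selection adds d points (assumed). The probability that the exact two-sided 5% test rejects upwards is:

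| Evaluable n | d = 0 | d = 5 | d = 10 |
|---|---|---|---|
| 112 (C1) | 0.022 | 0.18 | 0.58 |
| 75 (C2) | 0.021 | 0.12 | 0.41 |
| 186 (C1 and C2 together) | 0.018 | 0.24 | 0.78 |

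**5. Direction for specificity.** The negatives include "patients without CVD who have other skin pathologic conditions of lower extremities that require differential diagnosis with CVD", and for these the photo must show the abnormality. They are hard negatives. C0s patients pictured at a site without signs are easy ones. The split within the 8 slots is not fixed, so discretion can move specificity either way.

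**The case against.** Four points on the other side deserve weight.

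- **The enrolment text is not permissive on its face.** Read literally, every patient who is eligible and consents is included, and inclusion is described before the clinical evaluation. A reader might infer that the documents let the phlebologist pick patients with the diagnosis in hand. They do not say so; only the photo is expressly placed after the evaluation. What stands is that a class cell cannot be filled knowingly until the class is known, and that no rule governs who fills it. The sentence on choosing the site in mixed-class patients is explicit, and is the firmest evidence.
- **A reader might infer that there is no rule for the site at all.** That is wrong: its type and the picture conditions are fixed. Missing are a rule for choosing among several eligible sites of one type, and a rule for mixed-class patients that does not depend on the quota.
- **A reader might infer that accuracy as a whole is inflated.** The documents do not support this. Upward bias is plausible for sensitivity but not demonstrated, and mimic conditions among the negatives could lower specificity. Nor do quotas by themselves bias sensitivity: sampling by class is a legitimate design, although it sets the predictive values, and the mix of negatives affects specificity.
- **There are partial mitigations.** Each phlebologist contributes only 20 patients, and section 1.14 presents results by site. These may reveal differences between sites, but not a tendency that all sites share.

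The illustrated bias also stays within both half-widths. That does not make it harmless, because it is systematic and the interval does not allow for it.

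**Conclusion.** The concern holds in a limited form. The quotas carry no consecutive-enrolment rule, and the choice of photographed site is open among eligible lesions and guided by the quota in mixed-class patients. Followed exactly, this can bias the accuracy estimates: probably upwards for sensitivity, in an undetermined direction for specificity.

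The size cannot be established from the documents. On the assumed 90%, 65% and 60% inputs, sensitivity rises by 2.5 to 7.5 points. The upper end nearly equals the C1 half-width and is below the C2 half-width. This illustration assumes that selection works through lesion clarity, that the app does better on clear lesions, and that data loss is spread evenly.

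**What to change.** **Enrolment (Methodology).** Require each phlebologist to approach consecutive eligible patients and enrol those who consent into each quota cell until it is full. Keep an anonymous screening tally (class, enrolled yes or no, reason), and report eligible patients not enrolled per cell. Because the tally covers people who have not consented, it should hold no identifying data.

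**Site of the photo (Methodology).** Replace the quota-guided choice with a preset rule: picture the site of the presenting complaint or, if several sites qualify, the first in a fixed examination order. C0s patients keep a site without signs, at a preset location. If the site selected by the rule belongs to a full cell, do not enrol the patient and record this in the tally.

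**Related mismatch to settle.** The quota list gives C3 no cell ("2 patients with CVD with classes other than C1-C2 (C4-C6"), while section 1.11 counts C3-6. The two should be reconciled so that consecutive C3 patients are handled uniformly.

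**Cost.** A paragraph or two of text and a short tally per site. The quotas, planned sample size, photographer, single visit and single photo stay as they are. Enrolment may be slightly slower, and the accuracy figures may be less favourable.

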## Patient management

The study does not implicate to routine management of patients with chronic venous disease (CVD). In particular, in this study the parameters that are usually evaluated during the examination of patients with classes C0-6 of CVD (C) will be gathered and evaluated in accordance to routine clinical practice, standards and measures.

### Inclusion criteria:

- Age over 18 years
- Written informed consent is provided
- Symptoms and signs of CVD or any other skin pathologic condition (s) of lower extremities for which a patient seeks for phlebologist's consultation
- Ability to fulfil the technical requirements for smartphones/ images

### Non-inclusion criteria:

- Patients with mental/ psychiatric disabilities who are not able to understand objectives of the study and therefore provide a signed consent to participate in the study.

### Exclusion criteria:

- Patient's decision to withdraw his/her consent to participate in the study at any moment of the study conduction.

## Data collection during the study

At single visit, investigating physicians (phlebologists) will be assessing and collecting parameters of interest which they should input in eCRF.

Following data will be collected at the visit: a signed consent form from a patient, demographic characteristics (age, sex), eligibility of a patient to the inclusion/ non-inclusion criteria, 1 (one) image of skin area of interest, conclusion on presence or absence of CVD or any other pathologic condition(s) made as a result of objective/ instrumental examination. In case there will be any information related to safety of a Servier drug provided, investigating physician will also collect the information and fill in the PV form (Appendix 1).

Investigating phlebologist will inform patients about their participation in this program using the Informed consent form . eCRFs filled by an investigating physician will be available for Servier medical affairs personal accountable for the study conduction. Personal data of each patient consented to participate in the study will be protected in accordance to the local legislation.

## DATA COLLECTION DURING THE STUDY

Type of data obtained	V1 visit (inclusion)
-----------------------	-------------------------

Informed consent form signed	+
Inclusion/ Non-inclusion criteria	+
Demographic data	+
Presence or absence of CVD with clinical class (CEAP) or presence or absence of any other pathologic condition associated with skin disorder of lower extremities (if applicable)	+
1 Image	+
Safety information (AE/ADR/SADR, if applicable)	+

## Safety considerations.

### 1. Definitions

#### 1.1 Pharmacovigilance information

Pharmacovigilance data include any unintended or adverse event associated with the use of a medicinal product in humans, whether or not considered drug related, including the following **special situations** (situations where no adverse event occurred but information needs to be collected):

- exposure during pregnancy or breastfeeding;
- overdose, abuse, misuse, off-label uses, medication error, occupational exposure (including professional one);
- suspected transmission of an infectious agent via a medicinal product;
- unexpected beneficial action of the drug;
- lack of the treatment efficiency of drug.

#### 1.2. Adverse Event (AE)

Adverse event is any untoward medical occurrence in a patient or a clinical-trial subject who received the medicinal product, which does not necessarily have a causal relationship with the use of this medicinal product.

An adverse event can therefore be any unfavourable and unintended sign (e.g. an abnormal laboratory finding), symptom, or disease temporally associated with the use of a medicinal product, whether or not considered related to the medicinal product.

#### 1.3. Adverse (drug) reaction (ADR)

Adverse reaction (synonyms: Adverse drug reaction, suspected adverse (drug) reaction, Adverse effect, Undesirable effect) is a response to a medicinal product which is noxious and unintended.

“Response” in this context means that a causal relationship between a medicinal product and an adverse event is at least a reasonable possibility.

Adverse reactions may arise from use of the product within or outside the terms of the marketing authorization or from occupational exposure. Conditions of use outside the marketing authorization include off-label use, overdose, misuse, abuse and medication errors.

